9.3 Variables

The sections below describe the theoretical aspects of relevant variables. Data sources and operational definitions are discussed in 9.4.

9.3.1 Exposure of Interest

Doses of MenACWY-CRM administered at a KPSC facility are considered as exposures of interest in children 2-23 months of age who are KPSC members. The exposure of interest is MenACWY-CRM vaccine given as part of routine clinical care in all medical centers in KPSC. This study is strictly observational. MenACWY-CRM will be the only meningococcal vaccine used in children 2-23 months of age to prevent *N. meningitidis* serogroup A, C, W135 and Y caused meningococcal disease in KPSC. While HCPs are

advised to follow ACIP immunization recommendations, decisions regarding vaccinations and vaccination schedule will be determined by the HCP and caregivers. The MenACWY-CRM vaccination recommendation will be implemented at all KPSC medical centers.

No special labeling will be required for the MenACWY-CRM vaccine used in this study. Other vaccines may be co-administered as consistent with clinical practice.

According to the ACIP recommendation, MenACWY-CRM is recommended for infants and toddlers 2-23 months of age with high risk of meningococcal disease. The recommended meningococcal vaccination schedules for these high risk populations are as follows: [10]

- Children with anatomic or functional asplenia (including sickle cell disease):
 1. For children younger than 19 months of age, administer a 4-dose infant series of MenHibrix or MENVEO at 2, 4, 6, and 12 through 15 months of age.
 2. For children aged 19 through 23 months who have not completed a series of MenHibrix or MENVEO, administer 2 primary doses of MENVEO at least 3 months apart.
- Children with persistent complement component deficiency:
 1. For children younger than 19 months of age, administer a 4-dose infant series of either MenHibrix or MENVEO at 2, 4, 6, and 12 through 15 months of age.
 2. For children 7 through 23 months who have not initiated vaccination, two options exist depending on age and vaccine brand:
 - a. For children who initiate vaccination with MENVEO at 7 months through 23 months of age, a 2-dose series should be administered with the second dose after 12 months of age and at least 3 months after the first dose.
 - b. For children who initiate vaccination with Menactra at 9 months through 23 months of age, a 2-dose series of Menactra should be administered at least 3 months apart.
- For children who travel to or reside in countries in which meningococcal disease is hyperendemic or epidemic, including countries in the African meningitis belt or the Hajj, administer an age appropriate formulation and series of Menactra or MENVEO for protection against serogroups A and W meningococcal disease. Prior receipt of MenHibrix is not sufficient for children traveling to the meningitis belt or the Hajj because it does not contain serogroups A or W.

- For children at risk during a community outbreak attributable to a vaccine serogroup, administer or complete an age- and formulation-appropriate series of MenHibrix, Menactra, or MENVEO.

Catch-up recommendation of MenACWY-CRM for persons with high-risk conditions is as follows:

For children who initiate vaccination with MENVEO at 7 months through 9 months of age, a 2-dose series should be administered with the second dose after 12 months of age and at least 3 months after the first dose.

9.3.2 Outcome(s)

Outcomes include medical events that require an emergency room visit or hospitalization in children 2-23 months of age within 6 months following any dose of MenACWY-CRM vaccination.

9.3.3 Other Variables

- Baseline characteristics: these data will be extracted from patients' medical records.
 - Date of birth, expressed as age at vaccination
 - Gender
- Underlying condition of the MenACWY-CRM vaccine indication (i.e., persistent complement component deficiencies, asplenia or other), if available.
- Vaccination history
 - Concomitant vaccinations (specify)
 - History of other vaccinations (specify)
 - Vaccinations occurring during the observation period (specify)

9.4 Data Sources

The study will be conducted using the KPSC Oracle Research Data Warehouse (RDW) which supports external and internal research projects conducted in the Department of Research & Evaluation, KPSC as well as patient care management programs. The data warehouse is an integrated and comprehensive resource. It contains information as far back as 1980, including records related to membership, benefits, utilization, pharmacy, vital signs, laboratory, vaccines, geocoding, mortality, and procedures.

Medical events will be searched in the electronic medical record (EMR). All care provided at KPSC is recorded using the EMR. All details of a patient encounter, including diagnoses, procedures, and physician's notes, are entered into the EMR at the point of care. All vaccinations are entered into the EMR when they are given, with vaccine, dose, manufacturer, and lot number entered at the time of vaccination.

9.4.1 Operational Exposure Definition

Vaccination information will be searched from vaccination records. Documented MenACWY-CRM vaccination record is considered as evidence of exposure.

The date of vaccine administration in the medical records is considered as the vaccination date. Age at vaccination will be extracted from date of vaccination and date of birth. Age at vaccination will be expressed in number of months after birth.

The first dose of MenACWY-CRM vaccination administered at a KPSC facility to a KPSC member 2-23 months of age is the starting point of observation period for each study individual.

For each individual, the observation period is defined as the time from the first dose of MenACWY-CRM vaccination up to 6 months after the last dose of MenACWY-CRM vaccination received between 2-23 months of age, disenrollment, death, or the end of data collection, whichever occurs sooner.

9.4.2 Operational Outcome Definition and Identification Process

Medical events occurring in emergency and inpatient settings within 6 months following a MenACWY-CRM vaccination will be searched in electronic medical records. Diagnoses occurring in any care setting (inpatient, outpatient, or emergency room) prior to the first dose of MenACWY-CRM vaccination will be searched in electronic medical records for evidence of pre-existing medical events.

Events with a history of the same diagnosis prior to the first dose of MenACWY-CRM vaccination will be excluded as a pre-existing condition. The medical records prior to the first dose of MenACWY-CRM will be searched for the same diagnosis code. As there will be a transition from International Classification of Diseases, Ninth Revision (ICD-9) to Tenth Revision (ICD-10) coding, in the event that the diagnosis following a MenACWY-CRM vaccination is coded using ICD-10, both the same ICD-10 code and an equivalent ICD-9 diagnosis code will be searched in the period prior to the first dose.

If a study subject is first seen in the emergency department and subsequently transferred to the hospital, this will be treated as a single episode of care. Multiple records of a single medical event will be consolidated and treated as 1 report.

Medical events are considered as eligible if they occur in eligible study subjects during the observation period and are not pre-existing conditions.

For each identified emergency department or inpatient visit the following information will be collected:

[figure not shown]
- Diagnosis of medical events
- Date of diagnosis: the date of the documented code after any dose of MenACWY-CRM vaccination is considered the date of diagnosis. The date of diagnosis is expressed as the number of days following the 1st, 2nd, 3rd, or 4th dose of MenACWY-CRM vaccination.
- Health care setting: hospitalization or emergency room visit

Process of medical events identification

Eligible medical events identification process is illustrated in Figure 1:

1. Children 2-23 months of age vaccinated with MenACWY-CRM will be identified by immunization records in electronic medical records.
2. Medical events will be searched up to 6 months following MenACWY-CRM vaccination in the electronic records of emergency department and inpatient care units in all medical centers of KPSC.
3. Diagnosis codes of medical events from these visits will be identified.
4. Pre-existing conditions will be excluded by automated search.
5. Medical charts of identified eligible events will be reviewed and described.

Figure 9.4.2-1: Process of eligible medical events identification

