9.7.4 Statistical Considerations

Misclassification of diagnosis

As this study focuses on medical events requiring hospitalization and emergency care among children 2-23 months of age enrolled as KPSC health plan members, it is unlikely that serious and acute outcomes would be missed or misclassified. Also, due to the ICD-9 to ICD-10 transition, both ICD-9 and ICD-10 codes may need to be searched to exclude pre-existing conditions. Some pre-existing conditions may be missed from the automated search due to imperfect mapping between ICD-9 and ICD-10.

Misclassification of exposure

Depending on the available data in the medical record database on the recording of a vaccination, it may be that not all vaccinations are given through the HMO, resulting in not all vaccination data being present in the medical record. However, loss of these data should not affect results because analyses are confined to those individuals with a recorded vaccine administration.

Missing Data

No imputation will be performed. We expect there to be a very low rate of missing data regarding population characteristics, such as age and gender, and diagnoses. The study uses electronic medical records as the source of information for diagnoses, so events that do not result in a medical visit may be missed. Subjects missing the stratification factors will be excluded from subgroup analysis where the stratification factor is unknown. We expect that most vaccines will be captured by the electronic medical record, with very little missing information. It is possible that some study subjects will have received meningococcal vaccine prior to joining the health plan, and these prior doses may not be captured. This number is expected to be small and not to have a material impact on the results.

Handling of Loss to Follow-up

We expect there to be minimal loss to follow-up due to the high retention of KPSC health plan members in this age group. Any loss will be addressed in the data analysis by the truncation of person-time in the event rate calculation.

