9.8 Quality Control

9.8.1 Validation

Vaccination and medical event data will be extracted directly from the electronic medical record, which is the legal record of all medical care received within the KPSC system. Records of vaccinations and medical events can only be entered by medical staff, and are assumed to be an accurate representation of care received. No validation will be performed regarding vaccination. Medical events will be individually reviewed in order to determine the primary reason for the encounter as well as whether the condition predated the first receipt of MenACWY-CRM.

All data in the study is extracted and maintained in the electronic database at KPSC. The database is maintained on a daily basis, and undergoes quality validations regularly. Only authorized study personnel with passwords can access to databases. Validations of data in the study database will include range and consistency checks.

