Appendix B: Underlying condition of vaccine indication

Vaccine recipients will be determined to have the following underlying conditions for vaccination if the associated diagnosis codes are present in the medical record six months prior to index vaccination, including the date of index vaccination.

1. Asplenia

Functional - Hemoglobinopathies (primarily sickle cell [SS or SC] disease)

ICD-9 Codes:

Diagnosis	ICD-9 Diagnostic Code
Sickle cell disease unspecified	282.60
HB-SS disease with crisis	282.62
Sickle cell thalassemia without crisis	282.41
Sickle cell/HB-C disease without crisis	282.63
Sickle cell/HB-C disease with crisis	282.64
Other sickle cell disease without crisis	282.68
Other sickle cell disease with crisis	282.69
Sickle cell thalassemia with crisis	282.42

ICD-10 Codes:

Diagnosis	ICD-10 Diagnostic Code
Sickle cell disease without crisis	D57.1
HB-SS disease with crisis, unspecified	D57.00
Sickle cell thalassemia without crisis	D57.40
Sickle cell/HB-C disease without crisis	D57.20
Sickle cell/HB-C disease with crisis, unspecified	D57.219
Other sickle cell disorders without crisis	D57.80

Other sickle cell disease with crisis, unspecified	D57.819
Sickle cell thalassemia with crisis, unspecified	D57.419
Hyposplenism	D73.0

Anatomic Asplenia

ICD-9 Codes:

Diagnosis	ICD-9 Diagnostic Code
Anomalies of spleen congenital	759.0

ICD-10 Codes:

Diagnosis	ICD-10 Diagnostic Code
Asplenia (congenital)	Q89.01
Congenital malformations of spleen	Q89.09
Acquired asplenia	Z90.81

2. Persistent Complement Component Deficiencies

ICD-9 Codes:

Diagnosis	ICD-9 Diagnostic Code
Other specified disorders involving the immune mechanism	279.8

ICD-10 Codes:

Diagnosis	ICD-10 Diagnostic Code
-----------	------------------------

Defects in the complement system	D84.1
----------------------------------	-------

Table 1: Study population selection

Population	Total (n)
Total number of persons within the KPSC cohort	
Total number of children 2-23 months old in the KPSC cohort	
Total MenACWY-CRM vaccine recipients among age 2-23 months	

Date tables created:

Period captured in the tables:

Report integrates the tables:

Table 2: Baseline Characteristics of MenACWY-CRM Recipients 2 to 23 Months of Age

Characteristic	Total	Number of doses received			
		One	Two	Three	Four
Age at first vaccination (months)	mean (sd) median Q1, Q3 (min - max)				
Age 2-6 months at first vaccination	n (%)				
Age 7-23 months at first vaccination	n (%)				
Gender					
Male	n (%)				

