Number of recipients experiencing multiple different hospitalization or emergency encounters							
N/A = Not Applicable							

Table 4b: Summary of Diagnosis Identification and Review

Event	Automated Algorithm			Physician Review			Diagnosis is continuation of an ongoing episode (g)	Diagnosis is a recurrence (h)	Total Diagnoses for Analysis (i=a-b-e-f-g)
	Potential diagnoses identified (a)	Excluded diagnoses based on pre-existing condition (b)	Diagnoses remaining from automated algorithm identification (c=a-b)	Diagnoses confirmed (d)	Diagnoses refuted (e)	Confirmed events with diagnosis determined to be prior to index vaccination (f)			
Specific diagnoses									
diagnosis 1									
diagnosis 2									
Diagnosis groupings									
grouping 1									
grouping 2									
Number of recipients experiencing a single diagnosis									
Number of recipients experiencing multiple different diagnoses									

N/A = Not Applicable

Table 5a: Frequency and rate of hospitalization and emergency events observed following vaccination with MenACWY-CRM

Event	Overall		Number of vaccines received prior to event							
			One		Two		Three		Four	
	Frequency n (%)	Rate (95% CI)*	Frequency n (%)	Rate (95% CI)*	Frequency n (%)	Rate (95% CI)*	Frequency n (%)	Rate (95% CI)*	Frequency n (%)	Rate (95% CI)*
Hospitalization only										
Emergency department only										
Emergency department and hospitalization										

*Events per 1000 person years

Table 5b: Frequency and rate of diagnoses observed following vaccination with MenACWY-CRM

Event	Overall		Number of vaccines received prior to event								Setting of initial presentation with the diagnosis*						First occurrence or recurrence			
			One		Two		Three		Four		Inpatient		Emergency		Both settings		First occurrence		Recurrence	
	Frequency n (%)	Rate (95% CI)*	Frequency n (%)	Rate (95% CI)*	Frequency n (%)	Rate (95% CI)*	Frequency n (%)	Rate (95% CI)*	Frequency n (%)	Rate (95% CI)*	Frequency n (%)	Rate (95% CI)*	Frequency n (%)	Rate (95% CI)*	Frequency n (%)	Rate (95% CI)*	Frequency n (%)	Rate (95% CI)*	Frequency n (%)	Rate (95% CI)*
Specific diagnoses																				
diagnosis 1																				
diagnosis 2																				
Diagnosis groupings																				
grouping 1																				
grouping 2																				
etc.																				

*Events per 1000 person years

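### A match to an undefined 'equivalent' ICD-9 code excludes a post-dose ICD-10 diagnosis automatically, and a wrong match cannot be put right because correction runs only the other way

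*Protocol*

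**What the plan says.** Protocol 9.4.2 and SAP 3.3.3 exclude an event as pre-existing if its diagnosis code is in the child's record, in any care setting, before the first dose. For ICD-10 events, "both the same ICD-10 code and an equivalent ICD-9 diagnosis code will be searched in the period prior to the first dose". SAP 5.1 restates the exclusion using the same ICD code only and does not mention equivalents.

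The order of work is set by the numbered steps in Protocol 9.4.2. Step 4: "Pre-existing conditions will be excluded by automated search". Step 5: "Medical charts of identified eligible events will be reviewed and described". The same section defines the term eligible: "Medical events are considered as eligible if they occur in eligible study subjects during the observation period and are not pre-existing conditions".

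SAP v2.0 Tables 4a and 4b follow this order. Column b (excluded as pre-existing) stands under the automated algorithm. Column c is a − b, and the physician review columns come after it.

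On mapping error, Protocol 9.7.4 says: "Some pre-existing conditions may be missed from the automated search due to imperfect mapping between ICD-9 and ICD-10". SAP 6.2 repeats this. Protocol 9.8.1 has the chart review determine "whether the condition predated the first receipt of MenACWY-CRM", and column f of both tables removes confirmed events found to predate the index dose. SAP 5.4 plans no sensitivity analysis.

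**The concern.** The automated search can go wrong in two ways. It can miss a condition that was already present, which leaves an old event in the counts. Or it can match a new diagnosis to a prior ICD-9 code that is not the same diagnosis, which takes a new event out of the counts. The plan describes the first error and has a step that repairs it. It does not mention the second, and the workflow offers no way back for an event so excluded.

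In a descriptive safety study the second error is the less welcome one, because it hides events. The cohort is small (SAP 3.2 expects 60 to 100 children with high-risk conditions), and SAP 5.3 and Table 6 describe a diagnosis only if it has at least five episodes. A few wrong exclusions could therefore change what is reported.

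**Working it through.** No figure in the documents rests on the code mapping, so there is none to reproduce. The check traces an event through the steps and the table formulas.

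**1. Route of an event.** By step 4 a matched event is excluded by program. By step 5 only eligible events go to chart review, and eligible already means not pre-existing. A matched event therefore does not reach the reviewer.

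**2. Accounting.** Table 4a: total = a − b − e − f. Table 4b: total = a − b − e − f − g. Here a is potential events, b automated exclusions, e refuted, f confirmed but dated before the index dose, and g (Table 4b) continuation of an episode. Every term after a is subtracted. No column returns an event from b.

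**3. The two errors compared.** Illustrative Table 4b input (assumed): a = 40, of which 20 are truly new and 20 pre-existing; e = g = 0.

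| Case | b | f | Total = 40 − b − f | Truly new |
|---|---|---|---|---|
| No error | 20 | 0 | 20 | 20 |
| 4 pre-existing diagnoses missed by the search | 16 | 4 | 20 | 20 |
| 4 new diagnoses wrongly matched | 24 | 0 | 16 | 20 |

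The first error is corrected through column f. The second is not.

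**4. Can an equivalent be non-identical?** The search rule does not say, and the plan itself calls the mapping imperfect. The only codes printed are in SAP Appendix B. It lists ICD-9 759.0 where ICD-10 has both Q89.01 and Q89.09, and ICD-9 279.8 ("Other specified disorders involving the immune mechanism") where ICD-10 has the specific complement code D84.1. Most of its sickle cell codes pair closely by label. This shows that one-to-one equivalence cannot be assumed. It does not show how often it fails.

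**5. Where the loss would fall.** SAP 5.1 treats an encounter as pre-existing only if all its diagnoses are. Table 5a therefore keeps any encounter with one new diagnosis, but a visit with a single diagnosis can be lost on one false match. Tables 4b, 5b and 6 count each diagnosis on its own and lack this protection. In Table 6, a diagnosis with five episodes that loses one falls to four and is not described.

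**6. Size under assumed loss.** The share wrongly excluded is not in the documents, so 5% to 30% is an assumed range. Take N = 100 with one person-year each, as in the SAP 3.2 precision table, and exact Poisson limits for e events: lower = χ²(0.025; 2e)/2, upper = χ²(0.975; 2e + 2)/2. With no loss this reproduces the SAP's own cells: 4.8–18.4 at a rate of 10 per 100 person-years, and 81.4–121.6 at 100.

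| Share lost | True rate 10 | True rate 100 |
|---|---|---|
| 5% | 9.5 (4.5–17.7) | 95 (76.9–116.1) |
| 10% | 9 (4.1–17.1) | 90 (72.4–110.6) |
| 20% | 8 (3.5–15.8) | 80 (63.4–99.6) |
| 30% | 7 (2.8–14.4) | 70 (54.6–88.4) |

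At a rate of 10 the shift stays well inside the no-loss interval. At 100, a loss of 20% or more puts the true rate just outside the reported interval.

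**The case against.** The strongest reply has four parts.

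- **No example of harm.** Appendix B classifies the vaccine indication at baseline and is not the map for the pre-existing search. Its examples are congenital or persistent conditions, for which exclusion would usually be right. This stands: the appendix shows only that non-identical codes exist.
- **Review may be wider than the steps suggest.** SAP 3.1 says that a physician will review every identified event, and Protocol 9.8.1 speaks of individual review. SAP 3.1 is in tension with step 5 and the table layout and should be reconciled with them. But its stated purpose is to settle the final diagnosis, and even if column b events were read, the formulas subtract all of b.
- **There are mitigations.** Encounters survive on one new diagnosis, and Table 4b reports column b for each diagnosis, so the number excluded is visible. Both stand. Column b is not split by type of match, however, so exclusions through an ICD-9 equivalent cannot be told apart.
- **Same-code matches can err too.** An acute illness coded before dose 1 removes a later, separate episode with the same code. This is true and is a wider feature of the exclusion rule, which the present change does not address.

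A reader might go further and infer that the ICD-9 search is systematically broader, that new diagnoses are in fact being lost, or that the share of false matches can be worked out from the number of ICD-10 codes per ICD-9 code or from how many children have records in both systems. The documents do not support this. The rule says equivalent, not broader. The transition date is not given. Having records in both systems is not the same as losing an event. A reader might also expect rates to drift with calendar time, but no event rate is planned by calendar time; Figure 1 shows vaccinations only.

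**Conclusion.** The point holds as a gap in procedure. Exclusion through an undefined equivalent ICD-9 code is automatic, comes before chart review and is not reversible under the table formulas. The acknowledged mapping error and its correction cover only missed pre-existing conditions.

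A loss needs three things together: an ICD-9 record before dose 1, an ICD-10 diagnosis after it, and a match between non-identical conditions. Its frequency is unknown from the documents, and the rates in the working rest on assumed loss shares. The effect is mainly on Tables 4b, 5b and 6. The conclusion also rests on the natural reading of steps 4 and 5 and of the tables, over the looser wording of SAP 3.1. It is a low-cost improvement, not a threat to the study.

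**What to change.** 1. In Protocol 9.4.2 and SAP 3.3.3, name the ICD-9/ICD-10 map and define equivalent. Bring SAP 5.1 into line.
2. Exclude automatically (column b) only when the same code appears before dose 1 within one code system.
3. Send matches made only through an ICD-9 equivalent to the existing physician reviewer. Remove them only in column f, when the same condition before dose 1 is confirmed. The Table 4a and 4b formulas need no change: in the wrongly matched case of the illustration, b returns to 20, f stays 0, and the total is 40 − 20 − 0 = 20.
4. In Protocol 9.7.4 and SAP 6.2, state that mapping error can run both ways.
5. Reconcile the review statement in SAP 3.1 with Tables 4a and 4b.

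The cost is wording in both documents and a small number of extra charts, in a cohort expected to include 60 to 100 children with high-risk conditions.

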9.3 Setting

The study will be conducted at Kaiser Permanente Southern California (KPSC), the largest managed care organization in Southern California, serving over 3.7 million members that are broadly representative of the diverse racial, ethnic and socioeconomic background of the source population in Southern California.[8] The racial/ethnic breakdown of the KPSC population is 41% Hispanic, 36% Non-Hispanic White, 11% Asian/Pacific Islander, 9% Black, and 3% other.

Prepaid, comprehensive health care is provided to KPSC members at 14 medical centers and over 200 satellite clinics. All health care encounters are tracked through electronic data systems, with detailed information on diagnoses applied, procedures performed, and

immunizations administered, regardless of setting. KPSC members may seek emergency medical care from outside health care providers. For outside providers to be reimbursed by the health plan for covered emergency care, claims have to be submitted with documentation of the episode of care, and that information is entered into the administrative data systems. Thus, the capture of care delivered to KPSC members by electronic data is very comprehensive.

KPSC health plan members can enroll through their employer or the employer of a family member, through individual and family plans, or through state or federal programs such as California Public Employees' Retirement System, MediCal, and Medicare.

The KPSC Regional Immunization Practice Committee (RIPC) makes recommendations to ensure appropriate use of vaccination and implementation of new ACIP immunization recommendations within KPSC. KPSC has a proactive immunization program that includes: 1) alerts in the electronic medical record that indicate which age-appropriate routine vaccines are due based on vaccines that the member has already received, 2) a policy of vaccinating at all visits, not just well child or physical exam appointments, and 3) giving immunizations on a walk-in basis without appointment and at no-cost nurse visits. Since there is no charge for immunizations for KPSC members, there is an incentive to receive immunizations within the KPSC system.

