9.6 Data Management

9.6.1 Data Processing

Data collection and retrieval will be performed using the HMO's standard procedures in agreement with GSK. Quality assurance measures as implemented at the HMO will be used.

Blinding

This study is an open-label study conducted in a routine medical care setting. Reviewers are not blinded to the patient identity or vaccination status. All study staff with access to protected health information are trained in procedures to protect the confidentiality of subject data.

Data linkage

An important aspect of the KPSC managed care environment is its integrated approach to the delivery of medical care. This approach depends on, and therefore facilitates, the development and maintenance of a large number of databases, linkable through a unique medical record number. These databases include those that track membership, encounters, claims, pharmaceuticals dispensed and appointments. They also include test results as well as text excerpts of their interpretation. There are also a number of derivative files that have been developed for research purposes, including those for disease identification, geocoding files and mortality follow-up files.

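### Protocol 9.3 (Setting) rests its capture claim partly on outside emergency claims, but the event search as written never names claims, so outside ED encounters would be missed while person-time continues

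*Protocol*

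**What the plan says.** **Basis for completeness.** Protocol 9.3 (Setting) states that "KPSC members may seek emergency medical care from outside health care providers". It adds that outside providers must submit claims "to be reimbursed by the health plan for covered emergency care", and that this information reaches the administrative systems. It concludes: "Thus, the capture of care delivered to KPSC members by electronic data is very comprehensive". Claims for outside hospital admissions are not described.

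**Outcome search.** Protocol 9.4 (Data Sources) says: "Medical events will be searched in the electronic medical record (EMR). All care provided at KPSC is recorded using the EMR". Step 2 of Protocol 9.4.2 confines the search to "electronic records of emergency department and inpatient care units in all medical centers of KPSC". SAP v2.0 sections 3.1, 3.3.3 and 5.1 use the EMR without the facility phrase. None of these places names claims.

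**History search.** Under Protocol 9.4.2, diagnoses from any care setting "prior to the first dose of MenACWY-CRM vaccination will be searched in electronic medical records for evidence of pre-existing medical events". SAP v2.0 section 3.3.3 has the same limit.

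**Data held.** Protocol 9.4 describes a research data warehouse "including records related to membership, benefits, utilization, pharmacy". On linkable systems, Protocol 9.6.1 says: "These databases include those that track membership, encounters, claims, pharmaceuticals dispensed and appointments". SAP v2.0 section 9.1 lists utilization among the study data. No passage ties these sources to event identification.

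**Person-time.** Under Protocol 9.7.3 and SAP v2.0 section 5.2, person-time for a dose stops six months after it, or earlier at the next dose, disenrollment, death or close of data collection. Outside care does not stop it.

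**Stated limits.** Protocol 9.7.4 and SAP v2.0 section 6.2 consider missed serious or acute outcomes unlikely. On events lost to capture, Protocol 9.9 mentions only children who move out of the region.

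**The concern.** ED visits are one of the two kinds of encounter that define the outcome, so outside emergency care is in scope. The completeness argument uses a source that the search rule leaves out. If the rule is followed literally, the numerator loses outside encounters and the denominator loses nothing, so the encounter rates in Table 5a tend to be too low. An outside ED visit that leads to a KPSC admission could also be filed under hospitalization only. The effect on the diagnosis rates in Table 5b is less certain, because the same diagnosis may also be coded at a KPSC encounter.

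If claims are in fact searched, a different gap opens. SAP v2.0 section 5.1 refutes a diagnosis when chart review finds no evidence of it in the medical record, and does not say whether claim documentation counts. Two programmers working from the same text could reach different counts.

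No hypothesis test is at stake. But counts and rates are the study's main output, and a reader of the report could not tell whether they describe all emergency and inpatient care or only care at KPSC facilities.

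**Working it through.** **1. Text comparison.**

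| Element | Source as written | Claims named? |
|---|---|---|
| Completeness argument, Protocol 9.3 (Setting) | Administrative data, including outside emergency claims | Yes |
| Outcome search, Protocol 9.4 and 9.4.2 step 2 | EMR; ED and inpatient units of KPSC medical centers | No |
| Outcome search, SAP v2.0 3.1, 3.3.3, 5.1 | EMR | No |
| Pre-dose-1 history, Protocol 9.4.2 and SAP v2.0 3.3.3 | EMR, any care setting | No |
| Linkable databases, Protocol 9.6.1 | General list | Yes, but tied to no search rule |

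Protocol 9.8.1 describes the EMR as the legal record of care received inside the KPSC system, which supports reading the EMR search as excluding outside care.

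**2. The plan's own figure.** SAP v2.0 section 3.2 tabulates expected 95% intervals, assuming one person-year per child. For x events, the exact Poisson limits are χ²(0.025; 2x)/2 and χ²(0.975; 2x+2)/2, divided by person-years. In the row of 100 per 100 person-years, N = 50, 100 and 150 give 74.2-131.8, 81.4-121.6 and 84.6-117.3, as printed. Ten of the 12 cells match to one decimal. The other two, both at N = 50, differ by about 0.05 (9.348 against 9.4, and 3.247 against 3.3).

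**3. Effect on the rate.** Let q be the share of eligible encounters seen only outside KPSC. Person-time is unchanged, so

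observed rate = true rate × (1 − q).

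The documents give no value for q; 5%, 10% and 20% are assumptions. For a true 100 per 100 person-years at N = 100 (100 person-years):

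- q = 5%: 100 × 0.95 = 95 (76.9-116.1)
- q = 10%: 100 × 0.90 = 90 (72.4-110.6)
- q = 20%: 100 × 0.80 = 80 (63.4-99.6)

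**4. Coverage.** With μ true expected events, coverage is the sum of Poisson probabilities with mean μ(1 − q) over all counts k whose exact interval contains μ. For μ = 100 those counts are 81 to 120.

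| Expected events μ | q = 0 | q = 5% | q = 10% | q = 20% |
|---|---|---|---|---|
| 100 | 95.5% | 92.9% | 84.1% | 47.0% |
| 60 | 96.1% | 94.9% | 90.3% | 68.7% |
| 10 | 97.5% | 97.6% | 97.3% | 95.6% |
| 6 | 96.3% | 96.3% | 96.1% | 94.8% |

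The values 100 and 60 are the SAP's illustrative row of 100 at the ends of its 60-100 estimate of children with high-risk conditions. The values 10 and 6 are the row of 10 at the same N.

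**5. Where this applies.** Table 5a splits encounters into hospitalization only, ED only and both, with no all-encounter row. If 60 or 100 is the total, each row holds fewer events and loses less coverage than the first two lines suggest. The proportional shortfall q is the same at any count; what changes is whether the interval is narrow enough for it to matter.

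**6. History search.** Missing earlier outside diagnoses could let a pre-existing condition through the automated step. Protocol 9.8.1 then has each event reviewed for whether the condition predated dose 1, and column (f) of Tables 4a and 4b is subtracted from the analysis total. Any upward effect is what survives that review. The documents give nothing to size it, so it is not quantified.

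**The case against.** The best case for the plan is that practice may be wider than the text. The study runs on the data warehouse, which holds utilization records, and claims are linkable. Protocol 9.3 says encounters are tracked whatever the setting. The process figure is not reproduced in the available text, and the data dictionary is a separate document. This stands: a reader might infer that the study actually missed outside care, and the documents do not show that. They show only that the written rule does not reach it.

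A reader might also infer that the data source is not stated at all. It is: the EMR. The difficulty is that this source is narrower than the completeness argument.

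A third tempting inference is that conditions known earlier only from outside care would be counted as new and offset the shortfall. Physician review and column (f) are aimed at that error, so it remains a possibility and cannot be used as a counterweight.

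It is also fair that the study is descriptive, tests nothing, and discloses outside emergency use in 9.3. But the disclosure supports completeness and is not presented as a limitation. Protocol 9.9 does not mention outside care.

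**Conclusion.** The point holds as a conflict between the capture statement and the search rule. Run as written, outside ED encounters are missed while person-time continues, and encounter rates tend to be low by the fraction q. The size is unknown because q is unknown. On the assumed values, the loss of coverage matters for rates resting on roughly 60 to 100 events when q is about 10% or more, and is slight at about 10 events or fewer.

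These figures assume one person-year per child (the SAP's own assumption), independent counts although the SAP allows repeat events per child, and exact Poisson limits as in the SAP table. SAP v2.0 section 5.2 names PROC GENMOD for the report. The row of 100 per 100 person-years is an SAP illustration and not a forecast.

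This should be corrected, because the rates are the study's main product and the correction is cheap. It does not invalidate the design.

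**What to change.** **Preferred.** In Protocol 9.4.2 and SAP 3.1, 3.3.3 and 5.1:

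- Define the source for both the outcome search and the pre-dose-1 history search as KPSC EMR encounters plus linked outside claims.
- Apply the rule that treats an ED visit leading to admission as a single event across both sources.
- In SAP 5.1, state that claim documentation counts as evidence, so a claims-only diagnosis is not refuted merely because there is no KPSC chart.
- Report the number of claims-only events in Tables 4a and 4b. This would also show how much the choice of source matters.

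**If claims will not be searched.** Label the rates as KPSC-facility rates, add outside care to Protocol 9.9, and qualify the capture statements in Protocol 9.3 (Setting), Protocol 9.7.4 and SAP 6.2.

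**Cost.** The preferred route needs a protocol amendment with sponsor agreement and ethics board approval (Protocol 10.5), revised SAP text, and a claims query covering two time windows. Claims-only diagnoses will be harder to verify than charted ones. The alternative needs changes of wording only, though changes to the protocol text still go through amendment.
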